### **5.1.3. Microbiologic Assessments**

Urine culture samples will be obtained at Screening or Day 1, Day 5, Day 7, the EOT Visit, the TOC Visit, the LFU Visit, and any time the patient is deemed to have failed while on therapy. In patients with concurrent bacteremia who receive blinded study drug on Day 8 to Day 14, urine culture samples will be obtained daily. Urine cultures will be performed by the local laboratory. Additionally, a urinalysis including urine dipstick analysis for leukocytes, nitrites, or a catalase test of the urine specimen, microscopic evaluation, specific gravity, and pH will be performed at Screening, Day 1, Day 3, Day 7, the EOT Visit, the TOC Visit, and the LFU Visit. Screening urinalysis will be performed by the local laboratory; all other urinalysis samples will be sent to the central laboratory.

A urine sample taken to support diagnosis or to treat a medical condition within 48 hours prior to the first dose of study drug can be used for baseline microbiologic assessments if the organism(s) cultured were obtained and stored for shipment to the designated central laboratory. Otherwise, a repeat urine sample for baseline microbiologic assessments is required.

A repeat urine sample for culture must be obtained prior to the start of study drug treatment for any patient enrolled in the study who has received a single dose of a short-acting antibiotic in the 24 hours prior to randomization or for patients who failed preceding antimicrobial therapy. This sample should be taken as close to randomization as possible (within 2 hours prior to randomization, if possible).

Urine culture samples must be obtained through 1 of the following methods that minimizes the risk of bacterial contamination:

- Clean-catch mid-stream,
- Newly-inserted Foley catheter (bag specimens are not permitted),
- Bladder needle aspiration, or
- Ureter aspiration.

Baseline urine cultures must grow 1 or 2 bacterial organisms, each at  $\geq 10^5$  CFU/mL. If a patient grows  $\geq 3$  organisms in the urine, the urine culture will be considered contaminated unless  $\geq 1$  of the organisms also grows in a concurrently obtained blood culture.

Two sets of blood culture samples must be obtained from 2 separate venipuncture sites at Screening. Each set is collected from a separate venipuncture and consists of 1 aerobic and 1 anaerobic blood culture bottle. Each set of blood cultures should be collected by direct venipuncture from independent sites approximately 15 to 30 minutes apart. If baseline blood cultures are positive and not considered contaminated, repeat blood cultures should be obtained daily until negative or if the patient is a treatment failure. To avoid unnecessary blood draws, the Investigator may wait until the result of the prior blood culture is known before performing the next blood culture.

The local laboratory will culture each sample for organism identification, quantification (urine only), and susceptibility testing. Any organism isolated from the blood or urine will be identified by genus and species by the local laboratory. Potential pathogen(s) cultured at the local laboratory from urine or blood samples will be sent to a designated central laboratory for confirmation of identification and susceptibility testing results.

Only those baseline potential pathogens that grow in the urine at  $\geq 10^5$  CFU/mL and deemed not to be contaminants will be sent to the central laboratory. Potential pathogens that grow in both the urine and blood will also be sent to the central laboratory prior to randomization.

For post-baseline urine cultures, only those potential pathogens that grow at  $\geq 10^3$  CFU/mL and deemed not to be contaminants will be sent to the central laboratory.

#### **5.1.4. Microbiologic Outcome**

##### **5.1.4.1. Per-Pathogen Microbiologic Outcome**

Microbiologic outcome at Day 5, EOT, and TOC will be programmatically determined for each pathogen isolated at baseline. Per-pathogen microbiological response categories are eradication, persistence, and indeterminate defined as following:

Microbiologic eradication: the demonstration that the baseline bacterial pathogen(s) is reduced to  $< 10^4$  CFU/mL according to the Food and Drug Administration (FDA) criteria and  $< 10^3$  CFU/mL according to the European Medicines Agency (EMA) criteria on urine culture and negative on repeat blood culture (if positive at baseline).

Microbiologic persistence: the urine culture grows  $\geq 10^4$  CFU/mL for the FDA ( $\geq 10^3$  CFU/mL for the EMA) of any of the baseline pathogen(s) identified at study entry and/or a blood culture demonstrates the same baseline pathogen(s). Patients who are a persistence at EOT will be considered a persistence at TOC.

Microbiologic indeterminate: no follow-up urine culture is available, or the follow-up urine culture cannot be interpreted for any reason, or the follow-up urine culture is considered contaminated. For a baseline blood pathogen, no follow-up blood culture is available.

A per-pathogen microbiological outcome will be determined at the LFU visit. Per-pathogen microbiological outcome categories are sustained eradication, presumed sustained eradication,

continued persistence, recurrence, and indeterminate. A per-pathogen microbiologic outcome of persistence at TOC will be considered a continued persistence at LFU defined as following:

Sustained microbiologic eradication: microbiologic eradication at the TOC Visit and the LFU Visit.

Presumed sustained microbiologic eradication: no urine culture was done at LFU and patient meets clinical criteria for sustained clinical cure.

Microbiologic continued persistence: a per-pathogen microbiologic outcome of persistence at the TOC Visit will be considered a continued persistence.

Microbiologic recurrence: urine culture grows  $\geq 10^4$  CFU/mL for the FDA ( $\geq 10^3$  CFU/mL for the EMA) of any of the baseline pathogen(s) identified at study entry and/or a positive blood culture at any time after documented eradication at the TOC Visit up to and including the LFU Visit.

Microbiologic indeterminate: no follow-up urine culture is available, or the follow-up urine culture cannot be interpreted for any reason, or the follow-up urine culture is considered contaminated and the patient is not a sustained clinical cure.

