Microbiologic indeterminate: no follow-up urine culture is available, or the follow-up urine culture cannot be interpreted for any reason, or the follow-up urine culture is considered contaminated. For a baseline blood pathogen, no follow-up blood culture is available.

Microbiologic Outcome (at the LFU Visit):

Sustained microbiologic eradication: microbiologic eradication at the TOC Visit and the LFU Visit.

Presumed sustained microbiologic eradication: no urine culture was done at LFU and patient meets clinical criteria for sustained clinical cure.

Microbiologic recurrence: urine culture grows $\geq 10^4$ CFU/mL for the FDA ($\geq 10^3$ CFU/mL for the EMA) of any of the baseline pathogen(s) identified at study entry and/or a positive blood culture at any time after documented eradication at the TOC Visit up to and including the LFU Visit.

Microbiologic continued persistence: a per-pathogen microbiologic outcome of persistence at the TOC Visit will be considered a continued persistence.

Microbiologic indeterminate: no follow-up urine culture is available, or the follow-up urine culture cannot be interpreted for any reason, or the follow-up urine culture is considered contaminated and the patient is not a sustained clinical cure.

SAFETY VARIABLES:

The safety parameters include the incidence, severity, causality, and seriousness of treatment-emergent adverse events (TEAEs) and the evaluation of changes from baseline in safety laboratory test results, ECGs, vital signs, and physical examinations.

STATISTICAL ANALYSES:**Efficacy:**Primary:

The number and percentage of patients in each treatment group with an overall success, failure, and indeterminate response will be determined. A 2-sided 95% confidence interval (CI) for the observed difference in the overall success rates (ETX2514SUL group minus placebo group [background imipenem/cilastatin therapy]) will be calculated using a continuity-corrected Z-statistic.

Secondary:

The number and percentage of patients in each response category for each of the secondary efficacy outcomes will be provided. Two-sided 95% CIs for the difference in outcome rates between the ETX2514SUL group and the placebo group (background imipenem/cilastatin therapy) will be provided.

Pharmacokinetics:

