**Table 1. Schedule of Procedures**

Procedure	Screening		Treatment							TOC	LFU
	-48 Hours to Day 1 [1]	Day 1	Day 2 [2]	Day 3 [2]	Day 4 [2]	Day 5 [2]	Day 6 [2]	Day 7 to Day 14/ EOT +1 Day [2]	7 Days Post-EOT ±1 Day [3]	7 Days Post-TOC ±2 Days [3]	
Informed consent	X										
Inclusion/exclusion criteria	X										
Medical/surgical history	X [4]										
Prior/concomitant medications	X [5]	X	X	X	X	X	X	X	X	X	
Demographics [6]	X										
Complete physical examination [7]	X		X	X	X	X	X	X [8]			
Limited physical examination [7]			X	X	X	X	X		X	X	
Vital signs [9]	X	X	X	X	X	X	X	X	X	X	
Assess clinical signs/symptoms	X	X	X	X	X	X	X	X	X	X	
Assess clinical outcome [10]								X [11]	X [10]	X [10]	
Randomization		X									
Pregnancy test [12]	X							X [13]			
Serum chemistry [14]	X	X		X		X		X [11]	X	X	
Hematology [15]	X	X		X		X		X [11]	X	X	
Urinalysis [16, 17]	X	X		X		X		X [11]	X	X	
12-lead ECG	X [18,19]				X [18]						
Blood cultures		X [20]	X [20]	X [20]	X [20]	X [20]	X [20]	X [20]	X [20]	X [20]	
Urine cultures	X [21,22]					X [21]		X [21]	X [21]	X [21]	
Administer study drug [23]		X	X	X	X	X	X	X			
Administer imipenem/cilastatin [24]		X	X	X	X	X	X	X			
Assessment of adverse events [25]	X	X	X	X	X	X	X	X	X	X	
PK samples		X [26]			X [26]						

- Screening procedures may be performed up to 48 hours prior to the first dose of study drug. All Screening procedures must be completed prior to randomization and the first dose of study drug (Day 1). All Screening laboratories will be performed at the local laboratory and may have been collected as standard of care within 48 hours prior to randomization, with the exception of serum creatinine determination, which must be obtained at the local laboratory within 24 hours of the first dose of study drug.
- Study procedures are only required on treatment days that the patient receives IV therapy. If EOT occurs before Day 14, study procedures are not required to be performed on subsequent days until the TOC Visit.
- The TOC Visit must occur 7 days (±1 day) after the EOT Visit. The LFU Visit must occur 7 days (±2 days) following the TOC Visit. The LFU Visit should be performed as an in-office visit; however, if the patient is unable to attend the LFU Visit at the site, then the patient may be contacted by telephone call for follow-up assessment of concomitant medications, clinical signs and symptoms, and adverse events.

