##### **5.1.2. Clinical Outcome**

Based on the assessment of signs and symptoms, the Investigator will choose 1 of the following clinical outcomes at the Day 5, EOT, and TOC Visits:

Clinical cure: complete resolution or significant improvement of signs and symptoms of cUTI or AP that were present at baseline and no new symptoms, such that no further antimicrobial therapy is warranted.

Clinical failure: symptoms of cUTI or AP present at study entry have not significantly improved or completely resolved, or new symptoms of cUTI or AP have developed and require the initiation of a non-study antibacterial drug therapy, or death.

Clinical indeterminate: insufficient data are available to determine if the patient is a cure or failure.

Based on the assessment of signs and symptoms, the Investigator will choose 1 of the following clinical outcomes at the LFU Visit:

Sustained clinical cure: met criteria for clinical cure at the TOC Visit and the LFU Visit.

Relapse: clinical cure at the TOC Visit but signs and symptoms of cUTI or AP are present at the LFU Visit.

Clinical failure: clinical failure at the TOC Visit carried forward to the LFU Visit or death between the TOC Visit and LFU Visit.

Clinical indeterminate: insufficient data are available to determine if the patient is a sustained clinical cure or clinical relapse.

Note: if a patient is a clinical failure at EOT, the patient is automatically considered a failure at the TOC and LFU Visits, and an assessment of clinical response by the Investigator will be listed as “failure at EOT.”

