#### **5.1.4.2. Per-Patient Microbiologic Outcome**

An overall per-patient microbiological response at Day 5, EOT, and TOC will be programmatically determined for each patient based on individual outcomes for each baseline pathogen. For a patient to have a microbiological response of eradication, the outcome for each baseline pathogen must be eradicated. If the outcome for any pathogen is persistence, the patient will be considered to have a microbiological response of persistence.

Microbiologic eradication: the outcome of all baseline pathogens must be eradication at the specified visit (Day 5, EOT or TOC).

Microbiologic persistence: the outcome of at least 1 baseline pathogen is persistence.

Microbiologic indeterminate: the outcome of at least 1 baseline pathogen is indeterminate and there is no outcome of persistence for any baseline pathogen.

An overall per-patient microbiological response at LFU will be determined for each patient and will be based on individual outcomes for each baseline pathogen. For a patient to have a microbiological response of sustained eradication, the outcome for each baseline pathogen must be sustained or presumed sustained eradication. If the outcome for any pathogen is recurrence, the patient will be considered to have an unfavorable microbiological response. A per-patient microbiologic outcome of persistence at TOC will be considered a per-patient continued persistence at LFU.

Sustained microbiologic eradication: the outcome of all baseline pathogens must be sustained eradication or presumed sustained eradication.

Microbiologic recurrence: the outcome of at least 1 baseline pathogen is recurrence.

Microbiologic continued persistence: a per-patient microbiologic outcome of persistence at TOC will be considered a per-patient continued persistence.

Microbiologic indeterminate: the outcome of at least 1 baseline pathogen is indeterminate and there is no outcome of recurrence for any baseline pathogen.

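### Presumed sustained eradication at LFU does not require eradication at TOC, so an m-MITT patient with no usable culture at TOC or LFU can be counted as an LFU microbiologic success

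*SAP*

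**What the plan says.** SAP 5.1.4.1 gives each baseline pathogen one of five outcomes at LFU. The culture-proven success looks at both visits: "Sustained microbiologic eradication: microbiologic eradication at the TOC Visit and the LFU Visit". The presumed success has two conditions: "no urine culture was done at LFU and patient meets clinical criteria for sustained clinical cure". The LFU outcome definitions in the protocol synopsis use the same wording: "Presumed sustained microbiologic eradication: no urine culture was done at LFU and patient meets clinical criteria for sustained clinical cure".

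The clinical condition needs no culture. SAP 5.1.2 has: "Sustained clinical cure: met criteria for clinical cure at the TOC Visit and the LFU Visit".

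SAP 5.1.4.2 pools the two kinds of success. For a patient to be a sustained eradication, "the outcome of all baseline pathogens must be sustained eradication or presumed sustained eradication".

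Persistence at TOC has its own rule in SAP 5.1.4.1: "A per-pathogen microbiologic outcome of persistence at TOC will be considered a continued persistence at LFU". SAP 5.1.4.2 repeats it at patient level. No corresponding rule says what happens at LFU to a pathogen that was indeterminate at TOC.

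A missing LFU culture alongside a clinical assessment is foreseen. Under the notes to SAP Table 1 (also Protocol 6.5), if a site visit is not possible, "the patient may be contacted by telephone call for follow-up assessment of concomitant medications, clinical signs and symptoms, and adverse events".

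The endpoint concerned, sustained microbiologic eradication at LFU in m-MITT and ME, is exploratory (SAP 6.3, Protocol 7.3).

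**The concern.** An outcome called sustained should presuppose that eradication was seen at the earlier visit. The culture-proven category does; the presumed category does not. A patient whose TOC culture is missing, contaminated or uninterpretable, who is followed by telephone at LFU and is clinically well at both visits, meets the presumed definition and enters the numerator.

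Two things are at stake. First, missing microbiology becomes a success at LFU, while for the primary endpoint SAP 8.2 treats an indeterminate outcome as a failure. The LFU rate can be biased upward, and unequally between arms if cultures are missing unequally. Second, microbiologic outcomes are derived by program, so two categories that both fit one patient need a stated order; otherwise the programmer decides.

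**Working it through.** The documents state no rate or share for this endpoint, so there is no figure to reproduce. The check is of the rules.

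**Enumeration.** For one urine pathogen, cross TOC outcome (eradication, persistence, indeterminate), LFU urine culture (negative, positive, not done, uninterpretable) and sustained clinical cure (yes, no): 3 × 4 × 2 = 24 states. Exactly three meet the presumed definition, all with no LFU culture and sustained clinical cure:

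| TOC outcome | Other LFU rule that applies | Result |
|---|---|---|
| Eradication | – | Presumed; reasonable |
| Persistence | Continued persistence | Non-success by the explicit rule |
| Indeterminate | None that carries TOC status forward | Presumed, pooled as success |

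The third row is the defect. Compare the same TOC-indeterminate patient with an LFU culture that is done. If it is negative, the patient is not a sustained eradication (that needs TOC eradication) and fits no LFU category. If it grows the baseline pathogen, recurrence does not apply either, because it requires documented TOC eradication. Having no culture gives a better result than having a negative one.

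**The LFU indeterminate definition.** It lists no culture available, culture not interpretable, and culture contaminated, and ends with the condition that the patient is not a sustained clinical cure.
- If that ending governs all three clauses, the patient in the third row is not indeterminate and counts as a success.
- If it governs only the contaminated clause, the patient is both presumed and indeterminate. But then every presumed pathogen is also indeterminate, since none has an LFU culture, and the presumed category would be empty if indeterminate took precedence.

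The first reading is therefore the more coherent, but the text does not settle it.

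**Scale (assumptions, not document figures).**
- About 80 patients are randomized 2:1 (SAP 3.1). If 60% to 100% enter m-MITT, the arms are 80 × 2/3 × 0.6 = 32 and 80 × 1/3 × 0.6 = 16, up to about 53 and 27. One reclassified patient moves the rate by 1/53 to 1/32 = 1.9 to 3.1 points on ETX2514SUL, and by 1/27 to 1/16 = 3.7 to 6.25 points on placebo.
- Inflation = (share TOC-indeterminate) × (share of those with no LFU culture and sustained cure). From 0.05 × 0.10 = 0.5 points to 0.15 × 0.50 = 7.5 points.
- Illustration of the LFU rate passing the TOC rate: 60 m-MITT patients, 45 eradicated at TOC (45/60 = 75.0%), all still eradicated at LFU, plus 4 in the third row: (45 + 4)/60 = 81.7%. In general, LFU exceeds TOC only when third-row patients outnumber those eradicated at TOC who are not LFU successes.
- Against the precision: with arms of 37 and 19 and assumed successes of 26 and 13, the continuity-corrected difference is 1.8 points (95% CI −27.7 to 31.4). Two extra third-row patients on ETX2514SUL (28/37) make it 7.3 (−21.8 to 36.3).

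**The case against.** Several stronger inferences are tempting, and the documents do not support them.

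- *TOC persisters count as successes.* They meet the presumed wording, but the continued-persistence rule assigns them, per pathogen and per patient. Persistence at EOT is treated as persistence at TOC, so EOT persisters are excluded too.
- *The affected patients were never shown to be eradicated.* Cultures are also scheduled at Day 5, Day 7 and EOT (SAP 5.1.3). Because EOT persistence carries forward, a TOC-indeterminate patient was eradicated or indeterminate at EOT. The text supports only this: eradication not shown at TOC or LFU.
- *Both analysis populations are affected alike.* ME requires an interpretable TOC urine culture (SAP 7.5). What remains there is the unusual case of a baseline blood pathogen with no follow-up blood culture.
- *The LFU rate will exceed the TOC rate.* The illustration is a best case, with no recurrence and no LFU loss among the 45.
- *The pooling contradicts the protocol.* The synopsis lists presumed as its own category but does not call it a non-success.

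Two further points against the concern are fair. The SAP's exploratory analysis text (8.11.4) is redacted and the visible part of Protocol 7.8 stops after sustained eradication, so separate tabulation may already be planned. The endpoint is also exploratory, in a study whose primary objective is safety, with descriptive efficacy and no power calculation. These limit the weight of the point. They do not remove the gap in the SAP definitions, which are visible in full.

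**Conclusion.** The point holds for one group: m-MITT patients who are microbiologically indeterminate at TOC, have no LFU urine culture and are sustained clinical cures. On the literal and more coherent reading they are LFU successes; on the other reading they fall in two categories with no order between them. Either way the rule needs correction.

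Under the assumed shares, the m-MITT sustained eradication rate is overstated by 0.5 to 7.5 points. That is small beside the width of the interval in the example, but in arms this size one patient is visible. The primary and secondary TOC endpoints do not change, and the ME rate hardly does.

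A separate, minor wording gap lies in the recurrence definition, which accepts growth of a baseline pathogen in urine "and/or a positive blood culture at any time after documented eradication at the TOC Visit up to and including the LFU Visit". The blood-culture clause names no organism, whereas the persistence definition asks for the same baseline pathogen. This would lower the sustained rate, not raise it, and is of little weight because repeat blood cultures are called for only when the baseline ones were positive, until negative or treatment failure.

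**What to change.** In SAP 5.1.4.1 and 5.1.4.2, before unblinding:

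1. Define presumed sustained eradication by three conditions: microbiologic eradication at TOC, no LFU urine culture, and sustained clinical cure. This also removes the overlap for TOC persisters.
2. Class TOC-indeterminate patients with no LFU culture as LFU indeterminate, a non-success. Do not carry every TOC indeterminate forward: an LFU culture that grows the baseline pathogen must still be scored as a microbiologic failure. Name the category for a TOC-indeterminate patient with a negative LFU culture, who at present has none.
3. State which clauses of the LFU indeterminate definition the closing clinical condition governs.
4. Report culture-proven and presumed sustained eradication on separate lines.
5. As a minor wording change, tie blood-culture recurrence to the baseline pathogen.

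The synopsis wording should be aligned. The cost is a few sentences and one extra table line; the reported LFU rate may fall slightly.

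### LFU microbiologic recurrence: the blood-culture limb names no organism, so an unrelated bacteremia can count as recurrence and the outcome categories overlap

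*SAP*

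**What the plan says.** SAP 5.1.4.1 defines recurrence at LFU, for each baseline pathogen, by urine growth above the threshold "of any of the baseline pathogen(s) identified at study entry and/or a positive blood culture". The blood limb with its time window reads "and/or a positive blood culture at any time after documented eradication at the TOC Visit up to and including the LFU Visit". The protocol synopsis uses the same wording.

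The persistence rule for Day 5, EOT and TOC, in the same SAP section, has a narrower blood limb: "and/or a blood culture demonstrates the same baseline pathogen(s".

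The favorable LFU category is "Sustained microbiologic eradication: microbiologic eradication at the TOC Visit and the LFU Visit". Eradication itself has a blood condition that applies only to patients whose blood was positive at baseline.

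SAP 5.1.4.2 carries the pathogen result up to the patient: "If the outcome for any pathogen is recurrence, the patient will be considered to have an unfavorable microbiological response".

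**The concern.** The organism qualifier appears in three of the four places where a reader would expect it: both limbs of persistence and the urine limb of recurrence. It is absent from the blood limb of recurrence. A programmer who follows the text would count any post-TOC positive blood culture as recurrence of the baseline uropathogen, whatever grew. Another, reading the rule as a per-pathogen outcome, would require the species to match. Both could say they followed the SAP.

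At stake are the correct coding of sustained microbiologic eradication at LFU (m-MITT and ME), the LFU per-pathogen results, and the risk that individual patients are adjudicated after the question has arisen in the data.

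**Working it through.** The plan states no recurrence rate, effect size or power for this endpoint, so there is no figure to reproduce. The check compares the definitions and then gives a scale.

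**Definitions side by side (SAP 5.1.4.1)**

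| Outcome | Urine limb | Blood limb |
|---|---|---|
| Persistence (Day 5, EOT, TOC) | baseline pathogen(s) | baseline pathogen(s) |
| Recurrence (after TOC, through LFU) | baseline pathogen(s) | any positive culture |
| Eradication (also used for sustained eradication) | baseline pathogen(s) below threshold | negative repeat culture, only if blood was positive at baseline |

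**Worked case.** A patient has *E. coli* in urine at baseline and negative baseline blood cultures. Urine is clean at TOC and LFU. Between those visits a blood culture grows a different species.

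1. Recurrence: eradication at TOC is documented and a later blood culture is positive. The literal rule is met for *E. coli*.
2. Sustained eradication: urine is below threshold at both visits, and the blood condition does not apply because blood was negative at baseline. This rule is also met.
3. Precedence: SAP 5.1.4.1 does not say which category wins for a pathogen. SAP 5.1.4.2 settles the patient's result only once recurrence has been assigned: "Microbiologic recurrence: the outcome of at least 1 baseline pathogen is recurrence".
4. With two baseline pathogens, the one unrelated isolate would satisfy the literal recurrence condition for both.

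**How often a relevant culture is taken.** SAP 5.1.3 states: "If baseline blood cultures are positive and not considered contaminated, repeat blood cultures should be obtained daily until negative". A patient bacteremic at baseline must already have a negative repeat culture to be eradicated at TOC. The schedule therefore requires no post-TOC blood culture in a patient eradicated at TOC. Protocol 6.5 lists blood cultures at LFU only where applicable and allows LFU contact by telephone.

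**Scale per patient.** Inputs: about 80 randomized 2:1 (SAP 4). The m-MITT share is not given; 60% to 100% is assumed. One reclassified patient moves an arm's rate by 1/n.

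| m-MITT share | n ETX2514SUL : placebo | ETX2514SUL | placebo |
|---|---|---|---|
| 60% | 32 : 16 | 1/32 = 3.1 points | 1/16 = 6.3 points |
| 80% | 43 : 21 | 1/43 = 2.3 points | 1/21 = 4.8 points |
| 100% | 53 : 27 | 1/53 = 1.9 points | 1/27 = 3.7 points |

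The ME Population is a subset of the m-MITT, so for a given trial the shift there is at least as large.

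**Against the precision of the comparison.** The continuity-corrected 95% half-width, with a common rate p in both arms, is 1.96 × √[p(1−p)(1/n₁+1/n₂)] + ½(1/n₁+1/n₂).

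- Widest case (32:16, p = 0.70 assumed): 1.96 × √(0.21 × 0.09375) + 0.0469 = 0.275 + 0.047, or 32.2 points.
- Narrowest case (53:27, p = 0.80 assumed): 1.96 × √(0.16 × 0.0559) + 0.0280 = 0.185 + 0.028, or 21.3 points.

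**The case against.** The strongest reply is that context supplies the missing qualifier. The rule sits under a per-pathogen heading, the patient result is built from the outcome of each baseline pathogen, and recurrence of a pathogen after its eradication naturally means that pathogen came back. Blood isolates are identified to genus and species, so the narrow reading can be programmed. This is probably what was meant, but it does not settle the matter, because the same section writes the qualifier out for persistence and omits it here. Protocol 7.8 says the per-patient LFU response is derived programmatically. The SAP uses that word only for Day 5, EOT and TOC, so the argument should not lean on it for the per-pathogen LFU rule.

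It can also be said that counting any late bacteremia as unfavorable is a conceivable conservative choice. That is true, but neither document states such an intent, and as a per-pathogen result it would still attach a recurrence to an organism that had not returned.

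The point about rarity stands in full: a qualifying culture would be taken ad hoc.

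A reader might go further and infer that an unrelated bacteremia necessarily turns an eradication into a recurrence. The documents do not support that. In the worked case both categories are met and the text does not choose between them. Nor is there a conflict between protocol and SAP, since the synopsis and SAP share the wording.

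**Conclusion.** The concern holds as a defect of definition. The blood limb of LFU recurrence is unqualified, it is inconsistent with the persistence rule beside it, and it leaves recurrence and sustained eradication overlapping for some patients with no stated precedence.

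The consequences are small. The endpoint is exploratory and the protocol describes the efficacy analyses as descriptive. The primary and secondary endpoints are set at TOC and use the qualified rule, so any inference that the main efficacy result is exposed is wrong. One patient moves an arm's m-MITT rate by 1.9 to 6.3 points, depending on arm and on the assumed 60% to 100% share, against a half-width of about 21 to 32 points at assumed rates of 70% to 80%. The documents give no basis for estimating how many such patients there will be, beyond the expectation of few.

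Two limits apply. The public text of protocol 7.8 stops after the first LFU category, and the SAP's exploratory analysis section (8.11.4) cannot be read, so a restriction placed there cannot be excluded. Nothing visible restricts the blood limb.

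**What to change.** Make three changes before unblinding:

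1. In SAP 5.1.4.1 and the protocol synopsis (and protocol 7.8 if it reads the same), require the blood culture in the recurrence rule to grow the same baseline pathogen(s). Keep the existing time window.
2. State that, for a given pathogen, recurrence takes precedence over sustained and presumed sustained eradication. This is still needed after the first change: a patient without baseline bacteremia whose baseline pathogen appears in blood after TOC, with clean urine at LFU, would otherwise still meet both categories.
3. List post-TOC bacteremia with a different organism separately, by patient and treatment group.

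The cost is a few words in each document and one listing. No new data are needed, because blood isolates are already identified to species. The downside is that a new bacteremia with a different organism no longer counts as unfavorable in this endpoint; the separate listing keeps it visible.
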